5.6 Consent Process

The research coordinator and a representative from the medical team will confirm the patient's eligibility for the study based on inclusion and exclusion criteria. The research coordinator or medical team representative may approach the patient in the clinic or use a remote method such as telephone or videoconferencing.. The patient will be provided the opportunity to review informational materials related to the study, which may include an informational video. The Research Coordinator will review the informed consent document with the patient; this will include reviewing the purpose of the study, study procedures, the risks and benefits of study participation and alternatives to study participation. Adequate time will be allowed for patients to ask questions and have these questions answered to their full satisfaction. Finally, patients will be asked to participate.

Patients willing to participate may need more time to decide on their clinical treatment plan with their provider. In these cases, the research coordinator may ask the patient for permission to re-approach for the

study after the clinical decision has been made. Alternatively, patients may be willing to participate but their treatment arm has capped enrollment. Patients may agree to be contacted by the research coordinator if enrollment slots become available.

All patients agreeing to participate will be asked to sign the informed consent form (ICF) either electronically or on paper and will be given a copy for their records. The HIPAA Authorization form will also be signed and a copy given to the patient for their records, following IRB guidance. For some partnering sites, HIPAA language will be incorporated into the informed consent document but for others, this will be a separate document.

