6.6 Electronic Medical Record Abstraction

Patients consenting to the study will have their EMR reviewed at pre-determined time points. Research coordinators will conduct an EMR review at baseline and for subsequent healthcare utilization events and clinical outcomes. Data collected will include variables relating to health history, transurethral resection of a bladder tumor (TURBT), medical management, laboratory values, imaging results, pathology findings, cystectomy, and adverse events.

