10.1 SAE Reporting

Participants will be monitored for SAEs throughout their study surveillance period (enrollment through up to four-year follow-up). The occurrence of an SAE may come to the attention of study personnel during study follow-up phone interview, by UW study staff personnel conducting follow-up, or by a study participant calling the study team or presenting for medical care. If an SAE comes to the attention of study personnel via patient, caregiver, or family report, the site research coordinator will be notified that an SAE form needs to be completed. The site research coordinator will then use the EMR to fill out the SAE form. The site PI will then complete the form and sign the form. The SAE form will then be submitted to the DCC who will provide it to the CISTO Executive Committee. The CISTO Executive Committee will review the SAE form and ask the site PI for additional clarification or specification as they see necessary.

SAEs are defined as one of the following conditions:

1. Death during the period of protocol-defined surveillance;
2. Life-threatening event related to the treatment or significant disability/incapacity related to the treatment;
3. Inpatient hospitalization (other than for cystectomy);
4. Prolonged hospitalization following cystectomy (14 days or more).

All SAEs will be:

1. Recorded on the SAE case report form;
2. Followed until satisfactory resolution or until the study investigators deem the event to be chronic or the participant to be stable;
3. Reported to the study investigators, the project managers, and site IRBs per their reporting guidelines.

CISTO is an observational study using procedures or treatments with well-established risk profiles. There is no reason to suspect the risk profiles in the proposed study population would differ. The number of adverse events and related unexpected serious adverse events (SAEs) will be summarized descriptively by arm, by grade and body system. The proportion of participants experiencing each toxicity will be summarized by maximum National Cancer Institute's Common Terminology Criteria for Adverse Events (NCI CTCAE) grade²¹ experienced, overall and by arm.

The local and systemic side effects associated with intravesical therapy will be graded according to the International Bladder Cancer Group's (IBCG) recommendations²² (percentage indicates incidence rate):

- Cystitis noninfective (33-80%)

- Hematuria (up to 90%)
- Urinary tract obstruction (rare)

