## 1.4 Enrollment Timing

A participant's study clock begins on the date of completion of the baseline survey entry date.

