## 1.6 Analysis Timing

To facilitate and expedite publication of the primary results within the allotted window of funding for CISTO, an analytic data set will be frozen on March 14, 2024. All baseline information will be included in the analytic data set, as well as all longitudinal follow-up data for patients were enrolled in CISTO on February 14, 2023 or earlier. Statistical analysis, tables, and figures will be generated by the data coordinating center and manuscript development will begin in conjunction with the CISTO Writing Committee who are not involved with patient care or outcome collection. Once data have been collected and cleaned for the final participant (estimated January 2025), a final analytic data set will be generated to refresh tables, figures, and associated details with reporting.

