## 8. Data and Safety Monitoring Plan (DSMP)

The CISTO Study adheres to a Data Safety Monitoring Plan. Given the minimal risk nature of this observational cohort study, monitoring is conducted by the study's Executive Committee. On a monthly basis, the Executive Committee reviews any data and safety events and procedures and determine recommendations for these events and procedures as appropriate, including identifying, reviewing, and reporting adverse events (AEs) and serious adverse events (SAEs) and unanticipated problems to the applicable Institutional Review Boards (IRBs) or other monitoring bodies. SAEs are defined as 1) death during the study period; 2) life-threatening event related to the treatment or significant disability/incapacity related to the treatment; 3) inpatient hospitalization (other than for cystectomy); and 4) prolonged hospitalization following cystectomy (14 days or more). The number of adverse events and related unexpected serious adverse events (SAEs) will be summarized by arm, by recruitment site, by grade, and by the National Cancer Institute's Common Terminology Criteria for Adverse Events (CTCAE) system organ class. In addition, for each toxicity, the proportion of affected participants overall and by arm will be summarized by the maximum CTCAE grade experienced. The interim review of SAEs will not lead to recommendations towards study recruitment or discontinuation.

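### Toxicity is summarised by arm as a crude proportion at maximum grade with no time window, although follow-up differs between patients, so the figures correspond to no defined risk

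*SAP*

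**What the plan says.** SAP 8 gives the toxicity measure: "for each toxicity, the proportion of affected participants overall and by arm will be summarized by the maximum CTCAE grade experienced". Protocol 10.1 has the same measure and describes the event counts in these terms: "The number of adverse events and related unexpected serious adverse events (SAEs) will be summarized descriptively by arm, by grade and body system". No window, person-time denominator or cumulative incidence appears in either section.

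The observation period is open. For serious events, Protocol 10.1 says: "Participants will be monitored for SAEs throughout their study surveillance period (enrollment through up to four-year follow-up". For other toxicities no period is written. Protocol 6.6 names the record review as a source of adverse events and says only: "Patients consenting to the study will have their EMR reviewed at pre-determined time points". Those time points are not listed.

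Data are cut by calendar date. In SAP 1.6, "an analytic data set will be frozen on March 14, 2024", with all longitudinal follow-up for patients enrolled by 14 February 2023. Later, "Once data have been collected and cleaned for the final participant (estimated January 2025), a final analytic data set will be generated", and the tables are refreshed from it.

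Time zero is in SAP 1.4: "A participant's study clock begins on the date of completion of the baseline survey entry date". SAP 4.3 recognises that treatment may be delayed after enrolment. Protocol 9.1 defines arms by the choice at enrolment and expects up to 20% of the medical-management arm to have a cystectomy by 12 months.

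**The concern.** Whether a patient was ever affected, and at what maximum grade, can only move upward as observation lengthens. A proportion pooled over patients with different follow-up is therefore not the risk at 12 months, 24 months or any other time. The plan does set limits elsewhere: SAP 3 heads its main list of secondary outcomes with a 12-month horizon, and SAP 4.2 gives a censoring rule for survival outcomes. Toxicity falls under neither.

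What is at stake is how the by-arm table will be read. Surgical harm may concentrate around the operation, while harm from repeated medical treatment may accrue. Which arm looks more toxic can then depend on a window that nobody has stated. Protocol 2.1 presents the treatment decision as a weighing of cancer control against morbidity and quality of life, so readers will take these percentages as risks.

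**Working it through.** The documents state no expected toxicity proportion, so there is no planned figure to reproduce. The first step uses the documents' dates. The event risks in steps 2 to 4 are assumptions that show direction and sensitivity.

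**1. Follow-up at the two cuts**
- 14 February 2023 to 14 March 2024 is 394 days; 394 / 30.4375 = 12.9 months. This is the minimum potential follow-up in the frozen follow-up set. Earlier enrollees have more; how much more is unknown, because the enrolment start date is not given.
- 14 February 2023 to January 2025 is about 23 months. If the final data set takes follow-up to that date (an assumption), the same patient moves from about 13 to about 23 months.

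**2. The same risk read at different follow-up lengths**

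With a constant rate and an assumed 12-month risk p, the proportion affected by month t is 1 − (1 − p)^(t/12).

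| Assumed 12-month risk | 13 months | 23 months | 24 months |
|---|---|---|---|
| 5% | 5.4% | 9.4% | 9.8% |
| 20% | 21.5% | 34.8% | 36.0% |
| 40% | 42.5% | 62.4% | 64.0% |

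For example, 1 − 0.8^(24/12) = 1 − 0.64 = 36.0%. With follow-up spread evenly over 13 to 24 months, the 20% case gives a pooled 29.0%, which is the risk at neither end. For a fixed set of patients the figure can only rise between cuts. The refreshed table also adds later enrollees with shorter follow-up, so the net movement is not predictable.

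**3. Contrast between arms with equal follow-up**

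Assume that cystectomy toxicity is all perioperative at 40%, and that medical-management toxicity accrues at a constant rate with a 12-month risk of 20% or 30%. Cystectomy minus medical management, in percentage points:

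| Follow-up in both arms | 40% v 20% | 40% v 30% |
|---|---|---|
| 12 months | +20.0 | +10.0 |
| 24 months | +4.0 | −11.0 |
| 36 months | −8.8 | −25.7 |

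At 24 months in the first case: 40 − 36.0 = +4.0. The sign changes through follow-up length alone. The 36-month row assumes that observation of that length exists.

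**4. Crossover**

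Arms are fixed at enrolment, so surgical events after crossover count in the medical-management arm. With the protocol's upper figure of 20% and the assumed 40% perioperative risk, 0.20 × 0.40 = 8% of that arm could have a surgical event by 12 months. Any later crossover adds more, so this component also depends on the window.

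**5. Feasibility of a 12-month window**

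Everyone in the frozen follow-up set has at least 12.9 months of potential follow-up, so a 12-month horizon is available at that cut apart from death, withdrawal and loss.

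**The case against.** The strongest reply is that this is a descriptive table within a monitoring plan. Toxicity is in no hypothesis and neither secondary-outcome list, and no effect on it is tested or modelled. That stands, and it makes this a reporting defect. It does not give the percentages a meaning: a descriptive proportion set out by arm still needs a stated period.

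A second reply is that Protocol 10.1 refers the reporting of cystectomy and immunotherapy events to earlier published reports, which might carry a window. They cannot be checked from the documents. The protocol itself states no window there, and the reference does not change the by-arm proportion rule.

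Two stronger readings are tempting and are not supported:
- A reader might infer that the arms have different follow-up, so that the table carries a follow-up artefact. The enrolment cap offers a mechanism, since Protocol 5.6 says: "Alternatively, patients may be willing to participate but their treatment arm has capped enrollment". But Protocol 9.1 recruits in blocks within sites, which tends to make the arms accrue together. Protocol 9.4 reports 40.9% cystectomy patients, hence 59.1% medical management, below the two-thirds limit overall. The cap may bind at some sites, but no gap in follow-up is shown.
- A reader might apply the four-year surveillance period to every toxicity. It is written for serious events only; for the rest the period is simply unstated.

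Nor do the documents support saying that all efficacy outcomes stop at 12 months: SAP 3 also plans outcomes to 48 months and beyond.

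**Conclusion.** The concern holds as a defect in how harm is reported. The planned proportions correspond to no defined risk, can change between the March 2024 and final data sets without a change in risk, and give a by-arm contrast that depends on follow-up length even with equal follow-up. This rests on the absence of a window in SAP 8 and Protocol 10.1 and on the calendar cuts in SAP 1.6. The dependence of the contrast on follow-up further assumes that toxicity timing differs between treatments or that crossover occurs; the protocol anticipates crossover.

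The size cannot be computed from the documents, because toxicity rates, the enrolment start date and follow-up by arm are not given. The illustrations show that the distortion could be large enough to reverse the apparent ordering of the arms; they do not show that it will. The primary quality-of-life analysis is unaffected.

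**What to change.** In SAP 8 and Protocol 10.1:

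1. Make the main by-arm safety summary the 12-month cumulative incidence of each toxicity by maximum grade, counted from the study clock, with death as a competing event and censoring at withdrawal or last contact. A plain 12-month proportion would leave early death and withdrawal unhandled.
2. Report later events separately, as cumulative incidence or per person-year.
3. Show follow-up time by arm beside each table.
4. Add a supportive summary timed from first treatment, because the clock starts at the baseline survey and treatment may start late.

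The 12-month window does not remove crossover; it fixes how much of it the headline figure contains, and the table should say so.

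The cost is SAP wording and a little more programming. Event onset dates are needed, and the documents do not confirm that they are collected for non-serious events, so this should be checked first. Later events would move to a second table.
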